11. MEASUREMENT OF EFFECT

The primary objective of this study is to evaluate the ORR of the study drug. Patients with measurable disease will be assessed by standard criteria. Patients will be re-evaluated at the end of cycle 2 and cycle 6, thereafter every 4 months, or every 6 months if a CR is achieved. Response will be evaluated with physical exam, computerized tomography (CT) and tissue biopsies as defined in the 2014 Lugano classification.(Cheson et al., 2014b) PET/CT is optional, but strongly encouraged.

Evaluation of response:

Definitions

Evaluable for toxicity: All patients will be evaluable for toxicity starting from Day 1 of Cycle 1.

Evaluable for objective response: Patients who have received at least 1 cycle of therapy, and have had their disease re-evaluated will be considered evaluable for response. These patients will have their response classified according to the definitions stated below (Table 3). Patients who exhibit objective disease progression prior to the end of cycle 1 will also be considered.

Disease Parameters

Measurable disease. Measurable lesions are defined as those that can be accurately measured in two dimensions (longest diameter to be recorded) as ≥ 20 mm with conventional techniques (PET/CT, MRI, x-ray) or as ≥ 10 mm with spiral CT scan. All tumor measurements will be recorded in millimeters (or decimal fractions of centimeters). Tumor volume will be recorded as the sum of the product of the diameters (SPD) of the largest predominant target lesions (for sites of measurable disease, see Appendix 7).

FDG avidity is based on comparison with background tissues. There is no specific SUV cut-off value that is considered indicative of response.

Non-measurable disease (evaluable disease). All other lesions (or sites of disease), including small lesions (<10 mm using spiral CT scan), are considered non-measurable disease. Bone lesions, ascites, pleural/pericardial effusions, lymphangitis cutis/pneumonitis, inflammatory breast disease, abdominal masses (not followed by CT or MRI), and cystic lesions are all nonmeasurable.

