Target lesions. All measurable lesions, up to a maximum of 6, that are representative of all involved organs, should be identified as target lesions and measured and recorded at baseline. If PET/CT is performed, target lesions should be selected on the basis of their FDG avidity (High SUV lesions will be prioritized, even if not the largest lesions), size (lesions with the largest SPD diameter) and their suitability for accurate repeated measurements (either by imaging techniques or clinically). An SPD for all target lesions will be calculated and reported as the baseline sum SPD. The baseline sum SPD will be used as reference by which to characterize the objective tumor response based on CT criteria.

Non-target lesions. All other lesions (or sites of disease) including any measurable lesions over and above the 6 target lesions should be identified as non-target lesions and should also be recorded at baseline. Measurements of these lesions are not required, but the presence or absence of each should be noted throughout follow-up.

Methods for Evaluation of Measurable Disease in NHL

All measurements should be taken and recorded in metric notation using a ruler or calipers. All baseline evaluations should be performed as closely as possible to the beginning of treatment and never more than 4 weeks before the beginning of the treatment.

The same method of assessment and the same technique should be used to characterize each identified and reported lesion at baseline and during follow-up. As a general rule imaging-based evaluation is preferred to evaluation by clinical examination when both methods have been used to assess the antitumor effect of a treatment.

Clinical lesions. Clinical lesions will only be considered measurable when they are superficial (e.g., skin nodules and palpable lymph nodes). In the case of skin lesions, documentation by color medical photography that includes a ruler to measure the size of the lesion, is recommended.

CT, PET/CT and MRI. These techniques should be performed with cuts of 10 mm or less in slice thickness contiguously. Spiral CT should be performed using a 5 mm contiguous reconstruction algorithm. This applies to tumors of the chest, abdomen, and pelvis. Imaging of head and neck tumors and those of the extremities will be performed according to institutional specific protocols.

Ultrasound (US) Will not be used for disease assessment

Response Criteria

Response assessment in NHL

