Abbreviations: 5PS, 5-point scale; CT, computed tomography; FDG, fluorodeoxyglucose; IHC, immunohistochemistry; LDi, longest transverse diameter of a lesion; MRI, magnetic resonance imaging; PET, positron emission tomography; PPD, cross product of the LDi and perpendicular diameter; SDi, shortest axis perpendicular to the LDi; SPD, sum of the product of the perpendicular diameters for multiple lesions.

* A score of 3 in many patients indicates a good prognosis with standard treatment, especially if at the time of an interim scan. However, in trials involving PET where de-escalation is investigated, it may be preferable to consider a score of 3 as inadequate response (to avoid under treatment). Measured dominant lesions: Up to six of the largest dominant nodes, nodal masses, and extranodal lesions selected to be clearly measurable in two diameters. Nodes should preferably be from disparate regions of the body and should include, where applicable, mediastinal and retroperitoneal areas. Non-nodal lesions include those in solid organs (eg, liver, spleen, kidneys, lungs), GI involvement, cutaneous lesions, or those noted on palpation. Nonmeasured lesions: Any disease not selected as measured, dominant disease and truly assessable disease should be considered not measured. These sites include any nodes, nodal masses, and extranodal sites not selected as dominant or measurable or that do not meet the requirements for measurability but are still considered abnormal, as well as truly assessable disease, which is any site of suspected disease that would be difficult to follow quantitatively with measurement, including pleural effusions, ascites, bone lesions, leptomeningeal disease, abdominal masses, and other lesions that cannot be confirmed and followed by imaging. In Waldeyer's ring or in extranodal sites (eg, GI tract, liver, bone marrow), FDG uptake may be greater than in the mediastinum with complete metabolic response, but should be no higher than surrounding normal physiologic uptake (eg, with marrow activation as a result of chemotherapy or myeloid growth factors).

†PET 5PS: 1, no uptake above background; 2, uptake \leq mediastinum; 3, uptake $>$ mediastinum but \leq liver; 4, uptake moderately $>$ liver; 5, uptake markedly higher than liver and/or new lesions; X, new areas of uptake unlikely to be related to lymphoma.

Overall Response Rate

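### With PET/CT, uptake can override size when target lesions are chosen, contrary to the Table 3 footnote; with more than six measurable lesions this can decide PR or SD on CT

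*Combined protocol and SAP*

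**What the plan says.** All the relevant text is in Section 11 of the combined protocol and SAP.

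- **Target lesions, general rule:** "All measurable lesions, up to a maximum of 6, that are representative of all involved organs, should be identified as target lesions". This sentence ranks lesions neither by size nor by uptake.
- **Target lesions, in patients who have PET/CT:** "target lesions should be selected on the basis of their FDG avidity (High SUV lesions will be prioritized, even if not the largest lesions". The same sentence then names size and suitability for accurate repeat measurement. The baseline SPD of the chosen targets then serves as the reference for response on CT criteria.
- **Measurable disease:** tumour volume is recorded as "the sum of the product of the diameters (SPD) of the largest predominant target lesions".
- **Table 3 footnote:** the measured lesions are "Up to six of the largest dominant nodes, nodal masses, and extranodal lesions selected to be clearly measurable in two diameters", with a preference for nodes from different regions. The CT row for stable disease (SD) also speaks of dominant lesions. The CT row for partial remission (PR) speaks only of target lesions.
- **Non-target lesions, including measurable ones beyond six:** "Measurements of these lesions are not required, but the presence or absence of each should be noted throughout follow-up".
- **Status of the scan:** "PET/CT is optional, but strongly encouraged". The synopsis and the Screening list in Section 4 call it preferred.

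The primary endpoint, ORR, is the sum of the CR and PR rates by best response. No sentence says whether the uptake rule or the size rule prevails.

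**The concern.** SPD is a size measure meant to track tumour burden, and CT-based PR requires it to fall by at least half. The set of lesions it is computed on should therefore not depend on whether an optional scan was ordered. Under the PET/CT sentence, a large mass with lower uptake can lose its place to smaller, hotter nodes. It then becomes a non-target lesion that need not be measured, and the CT percentage describes the smaller nodes.

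This is a different question from which column of Table 3 (metabolic or CT) decides response, because it alters the CT result itself. At stake is the PR/SD call, and through it the primary ORR, in a trial of 20 patients where one call is worth 5 points.

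**Working it through.** **1. The plan's own figure.** Inputs from Section 13: N = 20, null ORR 0.33, alternative 0.60, one-sided alpha 0.10, power 87%. With X binomial, take the smallest r for which P(X ≥ r | 20, 0.33) ≤ 0.10.

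- r = 9: 0.182, too large.
- r = 10: 0.0866, acceptable. Power = P(X ≥ 10 | 20, 0.60) = 0.8725.

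The stated 87% is reproduced. The cut-off of 10 of 20 is implied by the exact test; the plan does not state it.

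**2. When the two rules differ.** With six or fewer measurable lesions, both rules take all of them and give the same SPD. They can differ only with more than six.

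**3. Formula.** Decrease = 1 − (follow-up SPD ÷ baseline SPD). On CT, a decrease of at least 50% is PR. A smaller one is SD if nothing meets the criteria for progression.

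**4. Illustration A (all lesion data assumed).** One 8 × 6 cm mass with low uptake (48 cm²) and six 2.0 × 1.5 cm nodes with high uptake (3 cm² each). The mass loses 20% of its area and the nodes 60%.

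| Targets | Baseline SPD (cm²) | Follow-up SPD (cm²) | Decrease | CT call |
|---|---|---|---|---|
| Six largest | 48 + 5×3 = 63.0 | 38.4 + 5×1.2 = 44.4 | 29.5% | SD |
| Six hottest | 6×3 = 18.0 | 6×1.2 = 7.2 | 60% | PR |

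**5. Illustration B, less extreme (also assumed).** Eight lesions with products 20, 18, 12, 10.5, 9, 7.5, 5 and 4 cm²; shrinkage 35, 35, 50, 55, 55, 60, 65 and 65%; SUV 5, 5, 9, 10, 11, 12, 13 and 14.

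| Targets | Baseline SPD (cm²) | Follow-up SPD (cm²) | Decrease | CT call |
|---|---|---|---|---|
| Six largest | 77.0 | 42.5 | 44.8% | SD |
| Six hottest | 48.0 | 20.9 | 56.4% | PR |

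**6. The shift can go the other way.** Take illustration A, but let the mass lose 60% and the nodes 20%. Six largest: 48×0.4 + 15×0.8 = 31.2, and 1 − 31.2/63 = 50.5%, PR. Six hottest: 18×0.8 = 14.4, a 20% decrease, SD.

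**7. Whether another rule catches it.** As Table 3 is printed, no CT row for PR requires non-measured lesions to shrink, so an unchanged non-target mass does not block PR. Clear progression of such a lesion does count as progressive disease, and CT-based CR requires non-measured lesions to be absent. The exposure is therefore mainly at the PR/SD boundary.

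**8. Consequence for the trial.** One patient is 1/20 = 5 points of ORR. At the implied boundary, 9/20 has one-sided p = 0.182 and 10/20 has p = 0.087. The table shows sensitivity to assumed shifts in the scored ORR, none of them estimated from the documents.

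| Assumed shift | Type I error of the 10/20 rule, ORR shifted up from 0.33 | Power, ORR shifted down from 0.60 |
|---|---|---|
| 2 points | 0.122 | 0.830 |
| 5 points | 0.190 | 0.751 |
| 10 points | 0.339 | 0.588 |

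**The case against.** The strongest reply is that this is a wording conflict with a narrow reach.

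- Uptake is not the only criterion with PET/CT. Size and measurability are in the same sentence, and targets must represent all involved organs. This stands, but the sentence expressly lets uptake win over size, and representativeness does not help when the mass and the hot lesions are all nodal.
- A reader might infer that the plan sets a size rule for patients without PET/CT. It does not say so in the target-lesion paragraph. The size rule comes from the Table 3 footnote and, more weakly, from the Measurable disease paragraph, which describes the SPD of lesions already called targets. This stands, and it leaves patients without PET/CT without a ranking in that paragraph.
- Patients with PET/CT may be scored in the metabolic column, where PR allows a residual mass of any size and SPD plays no part. The documents do not settle which column governs. Section 11 does tie the SPD of uptake-selected lesions to CT criteria, so the conflict matters wherever CT criteria are applied.
- Illustration A is extreme: the mass is 48 of 66 cm², or 73% of measured area, and every node is hotter than it. Illustration B shows that a flip does not need this, but it too is invented.

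**Conclusion.** The conflict is real, and it should be resolved because it touches the primary endpoint. The conclusion is limited to patients who have more than six measurable lesions, had PET/CT at baseline and are scored on CT criteria. In such a patient the PR/SD call can turn on whether the optional scan was ordered.

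The possible size is 5 points of ORR per reclassified patient, and one patient can carry the result across the implied 10/20 line. The illustrations show that a flip is possible, not how often it occurs. The documents give neither the number of patients with more than six measurable lesions, nor how often PET/CT will be done, nor any relation between uptake, size and shrinkage.

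Two stronger readings are tempting, and the documents support neither. One is that the rule inflates ORR: step 6 shows that it can also lower it, and no direction can be derived. The other is that the two centres will measure different things: nothing documents a difference between them in PET/CT use. The sample size, the 87% power and the implied cut-off are not in question.

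**What to change.** Reconcile the Target lesions paragraph, the Measurable disease paragraph and the Table 3 footnote by stating one selection rule for the CT-based SPD, fixed at baseline and applied whether or not PET/CT is done. To match the Table 3 criteria that the protocol adopts:

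- Choose at most six lesions, taking the largest dominant ones that can be measured clearly in two diameters, preferably from different regions.
- Remove the clause that gives high-SUV lesions priority over larger ones.
- Where PET/CT exists, use FDG uptake to confirm that a candidate lesion is lymphoma, and record the SUV of targets descriptively.

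The cost is about one sentence in Section 11 and a matching change to the baseline tumour form. Sample size and power stay as they are. The small downside is that the hottest lesion may not be a size target, though it is still recorded as a non-target lesion and seen on PET. If any patient already has targets chosen under the uptake clause, reselect them from the baseline CT without reference to follow-up scans, and report any change of response category.

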12. DATA REPORTING / REGULATORY REQUIREMENTS

Adverse event lists, guidelines, and instructions for AE reporting can be found in Section 7.0 (Adverse Events: List and Reporting Requirements).

Data Reporting

Monitoring

The Institutional Review Board (IRB) at Columbia University Medical Center will monitor this study.

Responsibility for Data Submission

The Study Coordinator is responsible for compiling data for all participants and for providing the data to the Principal Investigator for review.

Data Safety Monitoring Board

The Herbert Irving Comprehensive Cancer Center at Columbia University Medical Center's Data Safety Monitoring Board (DSMB) will oversee conduct of the study, patient safety and all interim analyses as specified in the data analysis plan. Detailed guidelines regarding the structure, function and decision-making mechanisms for the Data Safety Monitoring Board are provided in the DSMB charter.

Investigator Reporting Responsibilities

The conduct of the study will comply with all FDA safety reporting requirements.

Study auditing

Investigator responsibilities are set out in the ICH guideline for Good Clinical Practice (GCP) and in the US Code of Federal Regulations.

Investigators must enter study data onto CRFs or other data collection system. The Investigator will permit study-related audits by TG Therapeutics or its representatives, IRB/EC review, and regulatory inspection(s) (e.g., FDA, EMEA, TPP), providing direct access to the facilities where the study took place, to source documents, to CRFs, and to all other study documents.

Protocol amendments

Any amendment to this protocol must be agreed to by the Principal Investigator. Amendments should only be submitted to IRB/EC after consideration of TG Therapeutics review. Written verification of IRB/EC approval will be obtained before any amendment is implemented.

Protocol deviations

When an emergency occurs that requires a deviation from the protocol for a subject, a deviation will be made only for that specific subject. A decision will be made as soon as possible to determine whether or not the subject (for whom the deviation from protocol was effected) is to continue in the study. The subject's medical records will thoroughly and completely describe the deviation from the protocol and state the reasons for such deviation. In addition, the Investigator will notify the IRB/EC in writing of such deviation from protocol and when possible deviation will not be implemented until IRB approval is obtained..

Non-emergency minor deviations from the protocol will be permitted after approval of the Principal Investigator.

13. STATISTICAL CONSIDERATIONS

Study Design/ Primary Endpoints

This is a phase 2 study of oral TGR-1202 in patients with relapsed or refractory follicular lymphoma. (See figure 1 for study plan flow chart)

Sample Size/Accrual Rate

The phase II will allow for a total accrual of 20 patients.

We estimate accrual of an average of 1-3 patients per month, with a goal of completing accrual within 12 months.

Based on the phase I study of TGR-1202, the ORR for TGR-1202 will be 60%. The ORR is 33% based on historical control drugs, such as lenalidomide. We estimate that 20 patients will be needed to have a power of 87% to reject the null hypothesis that $ORR=0.33$ in favour of alternative hypothesis $ORR=0.6$ with one side type I error rate of 0.10.

Analysis of Primary and Secondary Endpoints

Disease and patient characteristics at baseline will be summarized using descriptive statistics. For qualitative variables, frequency distributions and proportions will be provided; for quantitative variables, summary statistics (e.g., mean, median, quartiles, standard deviations, etc) and graphical

displays (e.g., box plots) will be used. Overall response rates will be measured upon completion of the study with exact 95% confidence intervals.

REFERENCES:

Ansell, S.M., Witzig Te Fau - Kurtin, P.J., Kurtin Pj Fau - Sloan, J.A., Sloan Ja Fau - Jelinek, D.F., Jelinek Df Fau - Howell, K.G., Howell Kg Fau - Markovic, S.N., Markovic Sn Fau - Habermann, T.M., Habermann Tm Fau - Klee, G.G., Klee Gg Fau - Atherton, P.J., Atherton Pj Fau - Erlichman, C., *et al.* (2002). Phase 1 study of interleukin-12 in combination with rituximab in patients with B-cell non-Hodgkin lymphoma.

Armitage, J.O. (1993). Treatment of Non-Hodgkin's lymphoma. *N Engl J Med* 328, 1023-1300.

Baiocchi, R.A., Alinari L Fau - Lustberg, M.E., Lustberg Me Fau - Lin, T.S., Lin Ts Fau - Porcu, P., Porcu P Fau - Li, X., Li X Fau - Johnston, J.S., Johnston Js Fau - Byrd, J.C., Byrd Jc Fau - Blum, K.A., and Blum, K.A. (2011). Phase 2 trial of rituximab and bortezomib in patients with relapsed or refractory mantle cell and follicular lymphoma.

Appendix 1. Ann Arbor Classification

Stage	Description
I	Involvement of a single lymph node region or lymphoid structure (eg, spleen, thymus, Waldeyer's ring)
II	Involvement of two or more lymph node regions on the same side of the diaphragm
III	Involvement of lymph regions or structures on both sides of the diaphragm
IV	Involvement of extranodal site(s) beyond that designated E

NOTES:

1. For each stage, A= no symptoms; B= Fever (>38C), drenching sweats, 10% body weight loss over 6 months 2.
- For Stages I to III: E = Involvement of a single, extranodal site contiguous or proximal to known noda site

Adapted from: Armitage JO. CA Cancer J Clin.2005;55:368-376.

Appendix 2. Revised Staging System for Primary Nodal Lymphoma

Stage	Involvement	Extranodal (E) Status
Limited		
I	One node or a group of adjacent nodes	Single extranodal lesions without nodal involvement
II	Two or more nodal groups on the same side of the diaphragm	Stage I or II by nodal extent with limited contiguous extranodal involvement
II bulky*	II as above with "bulky" disease	Not applicable
Advanced		
III	Nodes on both sides of the diaphragm; nodes above the diaphragm with spleen involvement	Not applicable
IV	Additional noncontiguous extralymphatic involvement	Not applicable

* A variety of sizes have been suggested for the definition of bulky disease in NHL. However, none of the proposed sizes have been validated in the current therapeutic era. Therefore, it is recommended to record the longest measurement by CT scan. Whether stage II bulky disease is treated as limited or advanced disease may be determined by histology and a number of prognostic factors.

NOTE. Extent of disease is determined by positron emission tomography-computed tomography for avid lymphomas and computed tomography for nonavid histologies. Tonsils, Waldeyer's ring, and spleen are considered nodal tissue.

Adapted from: Cheson BD, Fisher RI, Barrington SF, et al. J Clin Oncol. 2014;32:3059-3067

Appendix 3. Eastern Cooperative Oncology Group (ECOG) Scale for Performance Status

Grade	Description
0	Normal activity. Fully active, able to carry on all pre-disease performance without restriction
1	Symptoms but ambulatory. Restricted in physically strenuous activity, but ambulatory and able to carry out work of a light or sedentary nature (eg, light housework, office work)
2	In bed < 50% of the time. Ambulatory and capable of all self-care, but unable to carry out any work activities. Up and about more than 50% of waking hours.
3	In bed > 50% of the time. Capable of only limited self-care, confined to bed or chair more than 50% of waking hours.
4	Bedridden 100% of the time. Completely disabled. Cannot carry on any self-care. Totally confined to bed or chair
5	Dead

Ref: Oken MM, Creech RH, Tormey DC, et al. Toxicity and response criteria of the Eastern Cooperative Oncology Group. Am J Clin Oncol 1982; 5 (6): 649-55

Appendix 4. Contraceptive Guidelines and Pregnancy

Women Not of Childbearing Potential are Defined as Follows:

Women are considered post-menopausal and not of child bearing potential if they have had 12 months of natural (spontaneous) amenorrhea with an appropriate clinical profile (e.g. age appropriate, history of vasomotor symptoms) or six months of spontaneous amenorrhea with serum FSH levels > 40 mIU/mL [for US only: and estradiol < 20 pg/mL] or have had surgical bilateral oophorectomy (with or without hysterectomy) at least six weeks ago. In the case of oophorectomy alone, only when the reproductive status of the woman has been confirmed by follow up hormone level assessment is she considered not of child bearing potential.

Contraceptive Guidelines for Women of Child-Bearing Potential:

Women of child-bearing potential, defined as all women physiologically capable of becoming pregnant, must use highly effective contraception during the study and for 30 days after stopping treatment. The highly effective contraception is defined as either:

- True abstinence: When this is in line with the preferred and usual lifestyle of the patient. Periodic abstinence (e.g., calendar, ovulation, symptothermal, post-ovulation methods) and withdrawal are not acceptable methods of contraception.
- Sterilization: have had surgical bilateral oophorectomy (with or without hysterectomy) or tubal ligation at least six weeks ago. In case of oophorectomy alone, only when the

reproductive status of the woman has been confirmed by follow up hormone level assessment.

- Male partner sterilization (with the appropriate post-vasectomy documentation of the absence of sperm in the ejaculate). For female patients on the study, the vasectomised male partner should be the sole partner for that patient.
- Oral contraception, injected or implanted hormonal methods.
- Use of a combination of any two of the following (a+b):
 - Placement of an intrauterine device (IUD) or intrauterine system (IUS).
 - Barrier methods of contraception: Condom or Occlusive cap (diaphragm or cervical/vault caps) with spermicidal foam/gel/film/cream/vaginal suppository.

The following are **unacceptable** forms of contraception for women of childbearing potential:

1. Female condom
2. Natural family planning (rhythm method) or breastfeeding
3. Fertility awareness
4. Withdrawal
5. Cervical shield

Women of child-bearing potential must have a negative serum pregnancy test within 5 days of initiating treatment.

Fertile Males:

Fertile males, defined as all males physiologically capable of conceiving offspring must use condom during treatment, for five half-lives (8 days) after stopping treatment and for additional 12 weeks (3 months in total after study drug discontinuation) and should not father a child in this period.

Pregnancies

To ensure patient safety, each pregnancy in a patient on study treatment must be reported to TG Therapeutics Inc. within 24 hours of learning of its occurrence. The pregnancy should be followed up for 3 months after the termination of the pregnancy to determine outcome, including spontaneous or voluntary termination, details of the birth, and the presence or absence of any birth defects, congenital abnormalities, or maternal and/or newborn complications. Pregnancy should be recorded on a Clinical Study Pregnancy Form and reported by the investigator to TG Therapeutics Inc. Pregnancy follow-up should be recorded on the same form and should include an assessment of the possible relationship to the study drug and reported by the investigator to TG Therapeutics Inc. Any SAE experienced during pregnancy must be reported on the SAE Report Form.

Pregnancy outcomes must be collected for the female partners of any males who took study treatment in this study. Consent to report information regarding these pregnancy outcomes should be obtained from the mother

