- 4) Relapse following first line immunotherapy or chemoimmunotherapy. There is no upper limit to the number of therapies received prior to study entry. Prior therapies may include high-dose therapy with autologous stem cell rescue.
- 5) Measurable Disease according to the Lugano classification (Cheson et al., 2014a). See Appendices 1 and 2.
- 6) Lymphoma that is amenable to safe pre-treatment and post-treatment biopsy. The safety of the procedures will be determined by the treating physician and the surgeon (or other proceduralist) in consultation with the PI, and in accordance with standard clinical practice. Acceptable sites of disease include, for example: (1) palpable tumor mass that is accessible under direct visualization or sonogram, (2) non-palpable tumor tissue that is accessible for biopsy under CT or sonogram guidance, (3) bone marrow.
- 7) Age ≥ 18 years
- 8) ECOG performance status ≤ 2 (see Appendix 3).
- 9) Patients must have adequate organ and marrow function as defined below:
 - a. absolute neutrophil count $\geq 1,000/\text{microliter}$
 - b. platelet count $\geq 50,000/\text{microliter}$
 - c. bilirubin $\leq 1.5X$ institutional upper limit of normal
 - d. aspartate transaminase (AST, SGOT)/alanine transaminase (ALT, SGPT) $\leq 3.0X$ institutional upper limit of normal
 - e. Serum creatinine $\leq 2.0X$ institutional upper limit of normal or creatinine clearance $\geq 50 \text{ mL/min}$ (according to the Cockroft and Gault equation).
- 10) Negative serum pregnancy test within 7 days prior to Cycle 1/Day 1 for women of childbearing potential.
- 11) All women of childbearing potential must agree to use an effective barrier method of contraception, as described in Appendix 4, during the treatment period and for at least 1 month after discontinuation of the study drug. Male subjects should use effective barrier method of contraception during the treatment period and for at least 1 month after discontinuation of the study drug (see Appendix 4).
- 12) Ability to understand and the willingness to sign a written informed consent document.

Exclusion Criteria

- 1) Grade 3B FL or evidence of transformation to a more aggressive lymphoma
- 2) Prior and concomitant therapy:
 - a. Prior exposure to any PI3 Kinase inhibitor
 - b. Exposure to chemotherapy, radiotherapy, or immunotherapy within 3 weeks prior to entering the study or lack of recovery from adverse events (AE) due to previously administered treatments.

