11. All women of childbearing potential must agree to use an effective barrier method of contraception, as described in Appendix 4, during the treatment period and for at least 1 month after discontinuation of the study drug. Male subjects should use effective barrier method of contraception during the treatment period and for at least 1 month after discontinuation of the study drug (see Appendix 4).
12. Ability to understand and the willingness to sign a written informed consent document.

Exclusion Criteria

1. Grade 3B FL or evidence of transformation of FL to a more aggressive lymphoma 2.

Prior and concomitant therapy:

- a. Prior exposure to any PI3 Kinase inhibitor
- b. Exposure to chemotherapy, radiotherapy, or immunotherapy within 3 weeks prior to entering the study or lack of recovery from adverse events due to previously administered treatments.
- c. Ongoing chronic pharmacologic immunosuppression, e.g. cyclosporine, or systemic steroids that have not been stabilized to the equivalent of ≤ 10 mg/day prednisone prior to the start of the study drug.
- d. Other concurrent investigational agents during the study period.

3. Prior allogeneic stem cell transplant
4. Central nervous system lymphoma, including lymphomatous meningitis
5. Acute intercurrent illness including, but not limited to, active infection, unstable congestive heart failure, unstable angina pectoris, psychiatric illness or any social situation that would limit compliance with study participation requirements in the judgement of the investigator
6. Major surgery performed within 4 weeks of study entry
7. Pregnant or nursing women
8. Active concurrent malignancy (except non-invasive non-melanoma skin cancer, carcinoma in situ of the cervix, or prostate intraepithelial neoplasia). If there is a history of prior malignancy, the patient must be disease-free for ≥ 3 -years at the time of study entry.
9. Documented Human Immunodeficiency Virus (HIV)-infection
10. Active hepatitis A, hepatitis B, or hepatitis C infection (see Appendix 5).
11. History of tuberculosis treatment within 2 years of study entry
12. Administration of a live vaccine within 6 weeks of first dose of study drug
13. Unable to receive prophylactic treatment for pneumocystis, herpes simplex virus (HSV), or herpes zoster (VZV) at screening
14. Prior surgery or gastrointestinal dysfunction that may affect drug absorption (e.g., gastric bypass surgery, gastrectomy)

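### Inclusion criterion 11 sets men a post-treatment contraception minimum of 1 month in both places it appears; Appendix 4 requires 3 months

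*Combined protocol and SAP*

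**What the plan says.** **Criterion 11, men.** The synopsis reads "Male subjects should use effective barrier method of contraception during the treatment period and for at least 1 month" after the study drug is discontinued. Section 3 (Inclusion Criteria) repeats the sentence, which there ends "for at least 1 month after discontinuation of the study drug (see Appendix 4".

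**Appendix 4, Fertile Males.** The rule opens "Fertile males, defined as all males physiologically capable of conceiving offspring must use condom during treatment" and continues "for five half-lives (8 days) after stopping treatment and for additional 12 weeks (3 months in total after study drug discontinuation". It adds that the man should not father a child during this period. Under Pregnancies, the same appendix states "Pregnancy outcomes must be collected for the female partners of any males who took study treatment in this study".

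**Women, for comparison.** Criterion 11 asks women of childbearing potential for "an effective barrier method of contraception, as described in Appendix 4, during the treatment period" and for at least 1 month afterwards. Appendix 4 says that they "must use highly effective contraception during the study and for 30 days after stopping treatment".

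**The concern.** The protocol gives two minimums for the same obligation, and the shorter one stands in the eligibility criterion. Section 4 has the Study Coordinator verify eligibility, so criterion 11 is the text that gets checked for each patient. A man or a site working to its figure would stop about two months before Appendix 4 allows.

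Nothing in the body of the protocol corrects the shorter figure:

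- The Pregnancy on Study part of Section 7 sets out duties for female patients and gives no period for men.
- The end-of-study visit in Section 5 falls 4 weeks ± 1 week after the last dose. That is about when the 1-month floor runs out, while the appendix rule still has about two months to go.
- Collecting outcomes of partner pregnancies records an exposure but does not prevent one.

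What is at stake is participant and partner safety, and consistent instruction of men. The statistical design is not involved.

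**Working it through.** **Inputs**

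- Criterion 11 (synopsis and Section 3), men: at least 1 month, taken as 30 days, with a range of 28 to 31 days.
- Appendix 4, men: 8 days plus 12 weeks, which the appendix totals as 3 months.
- Women: 1 month in criterion 11 and 30 days in Appendix 4.

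**Step 1. Reproduce the appendix total.** 8 + 12 × 7 = 8 + 84 = 92 days. Three calendar months are 89 to 92 days, so the stated total of 3 months agrees with its components.

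**Step 2. Gap for men.** 92 − 30 = 62 days, or about two months. The counting convention hardly changes this:

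| Convention | Gap (days) |
|---|---|
| 92 days minus 30 days | 62 |
| 92 days minus one calendar month (31 or 28 days) | 61 to 64 |
| 3 calendar months minus 1, same last dose | 59 to 62 |
| Month lengths varied separately (89 − 31; 92 − 28) | 58 to 64 |

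The last row is an outer bound. Both periods run from the same last dose, so its extremes are somewhat artificial.

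**Step 3. Criterion minimum as a share of the appendix period.** 30/92 = 33%, with a range from 28/92 = 30% to 31/89 = 35%.

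**Step 4. Compare the terms of the two rules.**

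| | Criterion 11 | Appendix 4 |
|---|---|---|
| Who | male subjects | fertile males, as defined there |
| Strength | *should* | *must* (condom use) |
| Method | effective barrier method | condom |
| After last dose | at least 1 month | 8 days + 12 weeks |
| Not fathering a child | not mentioned | *should not*, same period |

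**Step 5. Can one man satisfy both?** Yes, if he follows the appendix, because 92 days is more than the 1-month floor. The reverse fails: stopping at 1 month meets the criterion and breaches the appendix.

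**Step 6. Women.** One month and 30 days agree, so the mismatch in duration is confined to men. There is a minor difference in method. Criterion 11 asks for a barrier. Appendix 4 counts a barrier only under "Use of a combination of any two of the following (a+b", that is, together with an intrauterine device or system, and it accepts hormonal methods alone.

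**The case against.** The strongest reply is that these are two minimums and not two incompatible rules. Criterion 11 sets a floor, says *should* for men, and sends the reader to Appendix 4, where the complete and stricter rule stands. To be misled, a man or site must ignore that cross-reference. What men are actually told is in the consent form, which is not in the reviewed copy, so no under-instruction is shown. The documents also do not say which period is intended; that the half-life-based one governs is an inference. Finally, the women's wording is a separate question of method, and criterion 11 already defers to Appendix 4 there.

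Much of this is fair and limits the point. The gap is a maximum, harm is not demonstrated, and the direction of the correction needs the sponsor's confirmation. The women's wording is a side note only.

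It does not remove the inconsistency. A cross-reference resolves matters when the criterion leaves the detail to the appendix. Here the criterion supplies its own, shorter number, and the appendix makes the longer one mandatory. No other text in the protocol reconciles the two.

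**Conclusion.** The concern holds. For men, the minimum in both copies of criterion 11 is about two months (62 days; 58 to 64 on any counting convention) below the period that Appendix 4 makes mandatory, and is about one third of it. A man reaches that gap only if he stops at the stated floor. How many of the approximately 20 patients are fertile men is not given.

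The mismatch itself can be read directly from the texts and needs no assumption. That Appendix 4 is the intended rule is an assumption. It is supported by the word *must* and by the half-life derivation, whereas the 1-month figure comes with no rationale. The Investigator's Brochure was not available to confirm it.

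This should be corrected as a participant-safety instruction. It does not affect the primary endpoint, sample size or analysis.

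**What to change.** In criterion 11, in both the synopsis and Section 3, replace the sentence on men with the Appendix 4 rule: fertile males, as defined in Appendix 4, must use a condom during treatment and for 3 months after the last dose (8 days plus 12 weeks), and should not father a child in that time. Giving the components next to the total avoids a shortfall of up to 3 days when three calendar months come to 89 days and not 92.

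This wording narrows the group from male subjects to fertile males. If the sponsor wants all men covered, keep male subjects and change only the period.

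Before the amendment, confirm against the Investigator's Brochure that the longer period is intended, and check that the consent form states the same one. As a minor tidy-up for women, replace the reference to a barrier method with highly effective contraception as listed in Appendix 4.

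The cost is a wording change to two copies of one criterion plus the consent check. Visits, sample size and analysis do not change.
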